- After receiving LEEP or cryotherapy, women will be given free condoms and advised to abstain from sexual activities for at least 4 weeks. Women will also be offered an information sheet on the treatment procedure and abstinence information to take home for their spouse or partner. Information includes treatment given, recommended abstinence period and reasons for abstaining from sexual intercourse. These information sheets will be optional to maintain patient confidentiality and safety, especially for people who have not disclosed their status.
- Patients undergoing randomization will have the following performed:

- Blood (10mls) will be drawn to check for HIV viral load and CD4 count
 - Cervix will be swabbed to assess the presence of Human Papillomavirus (HPV) prior to LEEP or cryotherapy
 - Cervix will be swabbed for HIV viral level prior to LEEP or cryotherapy
 - LEEP or cryotherapy performed based on randomization envelope
 - Those undergoing LEEP will have the LEEP piece taken for histology
 - “Randomization” questionnaire completed
 - “Treatment” questionnaire completed
4. First, second, and third-week visits for cervical HIV-1 SHEDDING after treatment (~400 patients) (see Study Flow II)
- Patients who have been randomized and received treatment (approximately 400 patients) will be followed every 1 week for 3 weeks AFTER the treatment intervention to assess healing and measure HIV-1 viral shedding from the cervix. These events can be called the 7-9, 8-10, and 9-11-week visit time points and will probably coincide with the eighth, ninth, and tenth week after enrollment. However, for purposes of measuring HIV viral shedding, it is most important that these time points occur 1, 2, and 3 weeks after the treatment intervention. These terms are consistent and are used for descriptive purposes. They will return 3 times over a 3-week interval and have the following performed:
 - Blood (10mls) will be drawn to check for HIV viral load
 - Cervix will be swabbed to assess the presence of HIV-1
 - “Shedding” questionnaire completed

Shedding information will be considered valid if it is obtained \pm 3 days of the scheduled visit. We will collect shedding information for the first three weeks after treatment but if a patient misses those visits but comes back within six weeks, we will still collect the samples just for comparison purposes.

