The sample size was calculated to detect a 10% difference in treatment outcomes between LEEP and cryotherapy (4% versus 14%)²⁶ with 80% power and a 0.05 significance level. Accounting for the possibility of a 20% loss-to-follow-up rate over two years, we estimated that 400 women with high grade lesions would need to be enrolled in the study with 200 women randomized to each arm. It is estimated that 200 women in each arm will allow detection of a 0.25 log₁₀ HIV virus level difference in cervical shedding between the two arms with greater than 90% power. Based on results from an ongoing cervical cancer screening study implemented at the Hope Center in 2009, our estimation of the prevalence of high-grade intraepithelial lesions is about 18%. Given this estimate and the number of women who are likely to be eligible for randomization, we calculate that we need to enroll 2,400 women for initial screening.

The primary analysis of the study will be to compare treatment outcomes between the LEEP and cryotherapy intervention arms in an intent-to-treat analysis. Treatment outcomes will be measured by Pap smears taken every 6 months during two-year follow-up. Pap smears demonstrating high-grade intraepithelial lesions will be considered positive and compared against negative or low-grade intraepithelial lesions. A Chi-square test will be used to compare the percentage of positive Pap smears between the intervention arms at 6, 12, 18, and 24 months. Secondary analyses will compare cervical HIV-1 RNA viral shedding between the treatment arms. A comparison of the average area under the curve (AAUCMB) of long-transformed HIV-1 RNA cervical viral loads will be performed between the two arms using an analysis of covariance (ANCOVA) model.

Our analysis will include contraceptive history as a potential confounder. While there has been some suggestion in the literature that HIV infectivity among women on oral

contraceptives is increased,^{33, 34} a recent study from the UW did not show a significant increase in levels of HIV RNA in cervical samples obtained from women on hormonal contraception.³⁵ A more recent multicenter randomized controlled trial performed in Asia and Africa also did not find an association between hormonal contraceptive use and increased HIV transmission.³⁶ However, increased viral shedding due to hormonal contraceptive use remains an important and interesting question and one that we will examine in our study.

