The analysis will control for immunological status through measurement of CD4 count as well as presence of and duration on antiretroviral medications. Given that the study will recruit patients from an antiretroviral treatment clinic, it is expected that the majority of subjects will be on antiretroviral medications (~75%). Type and duration of antiretroviral drugs (ARVs) will be obtained through accessing clinical medical files and CD4 count measurements will be obtained regularly during study follow-up. The impact of ARVs on recurrence of cervical intraepithelial lesions is unclear and may have minimal effect.^{37, 38} Also, despite ARV use, HIV shedding has still been detected in the genital tract.³⁹ Therefore, we are confident that the sample size will still be adequate to detect differences between treatment modalities among women on antiretroviral medications.

Data Management

Introduction

Data will be captured on paper forms or electronically using Open Data Kit (ODK) application which has a data collection component to be used on a mobile device, and a centrally managed data store component. ODK is supported by the University of Washington (UW). Data will be cleaned, and analyzed at UW project offices located at KNH in Nairobi, Kenya. This office, which supports several UW studies, will provide administrative and database management support to this research project. Study data will be collected separately from Hope clinic data and will not be linked to the Hope dataset. The forms have been used in a recent cervical screening study and improvements have been made as a result. Analysis of the data will be conducted using SPSS version 16.0 (SPSS Inc, Chicago, Illinois, USA) by UW statisticians and epidemiologists associated with the study. Data will be managed by the Data Manager and the data clerk.

See Appendix B for data collection forms

Facilities

Cervical Cancer Screening room at Coptic Hope Center for Infectious Diseases

The on-site facilities available for cervical cancer screening include two examination beds, one office desk, and one computer, and at least one tablet PC. Electronic and paper data collection forms and paper informed consent forms will be administered here. The address and intake form, which captures patient identifier data will be completed on paper forms only.

UW study clinic and laboratory at Coptic Hope Center for Infectious Diseases

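### The shedding ANCOVA does not name the pre-treatment cervical HIV-1 RNA swab as a covariate; adding it recovers precision at no cost

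*Combined protocol and SAP*

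**What the plan says.** The second objective compares cervical HIV-1 shedding between cryotherapy and LEEP over three weeks. Statistical Methods lists this as a secondary analysis and gives it one sentence: "A comparison of the average area under the curve (AAUCMB) of long-transformed HIV-1 RNA cervical viral loads will be performed between the two arms". The method named is ANCOVA. No covariate appears in that sentence. AAUCMB is not expanded, and no AUC rule or time window is given.

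The adjusters follow in the same section: "Our analysis will include contraceptive history as a potential confounder", and then "The analysis will control for immunological status through measurement of CD4 count as well as presence of and duration on antiretroviral medications". Neither statement mentions the woman's own cervical HIV-1 RNA before treatment.

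That measurement is planned. Study Procedures, item 3 (randomization visit), states: "Cervix will be swabbed for HIV viral level prior to LEEP or cryotherapy". Item 4 adds swabs at three weekly visits and stresses that "it is most important that these time points occur 1, 2, and 3 weeks after the treatment intervention".

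On sample size, Statistical Methods states that "200 women in each arm will allow detection of a 0.25 log₁₀ HIV virus level difference" with power above 90%. It gives no standard deviation and does not say whether the difference refers to a single swab, a mean or an AUC.

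**The concern.** A pre-treatment value of the outcome variable is usually the strongest single predictor of its post-treatment values, and it is the usual covariate in an ANCOVA of repeated measurements. Here it is collected but not named, while other adjusters are. An analyst who follows the text literally would fit treatment arm, contraceptive history, CD4 count and ART, and leave the baseline swab out.

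Precision on a stated objective is at stake. Subtracting baseline does not replace adjusting for it. Subtraction forces a slope of one on a noisy single swab, so when the correlation between swabs is modest it adds variance. Ignoring baseline altogether leaves between-woman variation in the error, which is worst when the correlation is high.

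**Working it through.** **The plan's own figure.** With 200 per arm, a 0.25 log10 difference and two-sided alpha 0.05 (sidedness is not stated), 90% power needs an outcome SD of at most 0.25 / (3.24 × √(2/200)) = 0.771 log10. No SD is given, so the power statement cannot be confirmed or refuted. What follows is therefore relative.

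**Inputs.** Swab times of 0, 1, 2 and 3 weeks come from Study Procedures. Three things are assumed:
- equal variance σ² at each time and one common within-woman correlation ρ (compound symmetry), with ρ = 0.3, 0.5, 0.7;
- a trapezoidal average AUC over weeks 0-3, with weights 1/6, 1/3, 1/3, 1/6;
- no allowance for CD4, ART or contraception.

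**Variances**, in units of σ². Each AUC variance is divided by (5/6)² = 25/36, so that all refer to the same constant week 1-3 difference:
- Week 1-3 mean with baseline as covariate: (1−ρ)/3 + ρ − ρ²
- AUC minus baseline, no covariate: (34/36)(1−ρ) ÷ (25/36) = 1.36(1−ρ)
- AUC including week 0, no covariate: [(10/36)(1−ρ) + ρ] ÷ (25/36) = 0.4 + 1.04ρ
- Either AUC with baseline as covariate: 0.36(1−ρ) + ρ − ρ²

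| | ρ = 0.3 | ρ = 0.5 | ρ = 0.7 |
|---|---|---|---|
| Week 1-3 mean, adjusted | 0.443 | 0.417 | 0.310 |
| AUC minus baseline, unadjusted | 0.952 | 0.680 | 0.408 |
| – ratio to first row | 2.15 | 1.63 | 1.32 |
| AUC with week 0, unadjusted | 0.712 | 0.920 | 1.128 |
| – ratio to first row | 1.61 | 2.21 | 3.64 |
| Either AUC, adjusted | 0.462 | 0.430 | 0.318 |
| – ratio to first row | 1.04 | 1.03 | 1.03 |

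**Power.** Where the first row has 90% power, another analysis has Φ(3.24/√ratio − 1.96):
- AUC minus baseline: Φ(0.25), Φ(0.58), Φ(0.87) = about 60%, 72%, 81%.
- AUC with week 0: Φ(0.60), Φ(0.22), Φ(−0.26) = about 72%, 59%, 40%.

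**In absolute terms**, with an assumed per-swab SD of 1.0, 200 per arm and a constant 0.25 difference at weeks 1-3, power at ρ = 0.3 / 0.5 / 0.7 is:
- AUC minus baseline: 0.727 / 0.858 / 0.975 without the covariate;
- AUC with week 0: 0.842 / 0.741 / 0.653 without the covariate;
- either AUC: 0.957 / 0.968 / 0.993 with the covariate.

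**Does the result depend on what AAUCMB means?** Once baseline is a covariate, the AUC and the AUC minus baseline differ only by a multiple of that covariate, so they give the same treatment estimate and the same test.

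If the AUC covers weeks 1-3 only (weights 1/4, 1/2, 1/4), its variance is 0.375(1−ρ) + ρ without the covariate and 0.375(1−ρ) + ρ − ρ² with it. At ρ = 0.5 that is 0.6875 against 0.4375, a ratio of 1.57. Omission costs precision on that reading too.

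**The case against.** The strongest reply is that ANCOVA with a pre-treatment swab on hand naturally means baseline-adjusted, and that the adjusters are not presented as a complete list for this model. That may be the intention. If so, the losses above do not arise and the clause merely records it. But the text names three other adjusters and not this one, so the intention cannot be read from it.

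Second, the planned CD4 and ART adjustment would recover some of the loss. This stands for the unadjusted AUC: removing shared between-woman variation lowers the residual correlation and moves that ratio towards its smaller values. It does not help the subtraction-only analysis in the same way, since its ratio is largest at low correlation.

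Third, the correlations are assumed. The calculation also ignores the assay's lower limit of 50 copies per swab, which may matter with about 75% of women expected on ART. Both affect the size of the loss. They do not reverse the direction so long as baseline and later swabs are positively correlated.

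A reader might go further and infer that the plan builds the pre-treatment swab into the outcome and so shrinks a real difference by one sixth. The documents do not support this:
- Reading the last two letters of AAUCMB as minus baseline is plausible, but it is not in the text.
- The one-sixth figure (0.25 × 5/6 = 0.208) needs both a trapezoid that includes week 0 and a constant difference at weeks 1-3. Under the same weights, the ratio to the week 1-3 mean runs from 0.50 (difference at week 3 only) to 1.00 (week 1 only). An AUC over weeks 1-3 does not shrink a constant difference.
- Where it applies, it is a change of scale and not a bias. It is the same with or without the covariate. After baseline adjustment the standardized effects nearly agree: 0.381 for the AUC against 0.387 for the mean, at SD 1.0 and ρ = 0.5.

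**Conclusion.** The point holds as an omission in the model specification. The plan does not name pre-treatment cervical HIV-1 RNA as a covariate, and an analysis that follows the text literally loses precision on every reading of the AUC examined here.

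Under compound symmetry with correlation 0.3 to 0.7, the variance is 1.32 to 2.15 times that of the adjusted week 1-3 mean if baseline is only subtracted, and 1.61 to 3.64 times if it is neither subtracted nor adjusted for. These figures come before any gain from the other adjusters and rest on correlations that the documents do not give.

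The check does not show that the stated power is wrong, that the estimate is biased, or that the AUC must give way to a mean. With baseline in the model, that last choice is worth only about 3-4% in variance. This is a secondary analysis, and the change is a free improvement to it.

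**What to change.** In Statistical Methods, add to the end of the ANCOVA sentence: *with pre-treatment log10 cervical HIV-1 RNA as a covariate, in addition to the planned covariates.*

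The cost is one clause and one degree of freedom among about 400 women. The swab is already planned, so no new data are needed. The AUC stays as the outcome, and the 0.25 log10 planning figure need not be reassigned to another scale.

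While the sentence is open, it would help to expand AAUCMB and state the AUC window. With the covariate in place, whether baseline is also subtracted no longer affects the test.

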5. Six, twelve, eighteen, and twenty-four months after randomization visits for RECURRENCE (approximately 400 patients) (see Study Flow II)

- After the 9-11-week visit, randomized participants and those who undergo LEEP but are not randomized because their lesions are not amenable to cryotherapy will return at 6, 12, 18, and 24 months after treatment is administered. At the 24 month visit, the subject will be exited from the study. At these 6-month interval visits, the following will be performed in order:
 - Pap smear to detect recurrence of cervical intraepithelial lesions
 - Same Pap smear swab will be used to assess the presence of Human Papillomavirus (HPV)
 - Blood (5 mls) will be drawn to check for CD4 count
 - “Pap Smear” questionnaire completed
- Pap smear results that are normal, ASCUS, will be filed in the participants file and disclosed at the next scheduled follow-up visit. If pre-cancerous lesions by cytology have recurred then patient will be contacted to return to the study clinic to undergo colposcopic directed biopsy prior to treatment. Results of the colposcopic examination will be entered in the “Colposcopy” questionnaire..
 - If histology-confirmed lesions can be treated by LEEP, then the patient will receive a free LEEP and “Treatment” questionnaire will be filled.
 - If histology-confirmed lesions are too large or cancerous for LEEP then patient will be referred to KNH for subsidized care at this government

hospital. The study will not pay for this treatment. Patients will be given follow-up appointments in the study clinic after referral to determine outcomes.

- Phone calls and home visits will be performed sequentially in the case of a subject who has been lost to follow-up (LTFU) after screening or randomization (see LTFU section). LTFU will be prepared and discussed at weekly clinic meetings. Written reports will be prepared from these meetings and sent to co-investigators. Home visits will be performed by community health workers trained to be discreet in their approach to finding patients. They will not wear clothes that would identify them as health workers and will only use public transportation or unmarked private vehicles. They may ask about the participant's health or whereabouts.

6. Specimen transportation

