No dysplasia (NIL)

CIN 1

CIN 2

CIN 3

Invasive carcinoma

Indeterminate/

CIS

Other, specify

10. Was there evidence of cervicitis? F Yes F No Other, specify

11. Who read the biopsy and gave this histology result?

Pathologist Interviewer number ____

12. Comments:

--

CD4 REPORT

Study ID Number

Hope ID Number

Visit (tick one) Randomization/LEEP Visit Month 6FU Month 12FU Month 18FU Month 24FU Other, specify

Patient Age

Interviewer number

1. Date sample was collected in clinic (day/month/year) / /
2. Time sample was collected in clinic
3. Date sample was received in laboratory (day/month/year) / /
4. Time sample was received in laboratory
5. When was the CD4 count run? (day/month/year) / /
6. What was the result of the CD4 count?
7. Who ran the CD4 count and gave this CD4 result? Coptic lab F Other, specify

8. Comments:

FOLLOW-UP FORM

Study ID Number _____ Hope ID Number _____ Interviewer Number _____

Date of interview (day/month/year) _____/_____/_____

Visit (tick one) Month 6 FU Month 12 FU Month 18 FU

Month 24 FU Other, specify _____

A: MEDICAL HISTORY

1. Did you consult a doctor or clinical officer between today and your previous study visit?

- Yes
- No (go to question 2)
- Don't know (go to question 2)
- Refused (go to question 2)

If yes:

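### The plan promises control for CD4 and ART, but its primary chi-square takes no covariates and no baseline-adjusted comparison of recurrence is specified

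*Combined protocol and SAP*

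**What the plan says.** Three places in the combined protocol and SAP bear on this.

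**The promise.** Statistical Methods: "The analysis will control for immunological status through measurement of CD4 count as well as presence of and duration on antiretroviral medications". The paragraph goes on to discuss both recurrence and HIV shedding. It takes ART type and duration from clinic files, with no reference date, and adds for CD4: "CD4 count measurements will be obtained regularly during study follow-up". The preceding paragraph also lists contraceptive history as a potential confounder.

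**The primary test.** The same section sets out to "compare treatment outcomes between the LEEP and cryotherapy intervention arms in an intent-to-treat analysis", and gives the method: "A Chi-square test will be used to compare the percentage of positive Pap smears between the intervention arms at 6, 12, 18, and 24 months". No covariate, stratum or regression model is named. The one model that can take covariates is the ANCOVA for the secondary shedding outcome. The loss-to-follow-up section mentions a survival analysis but does not specify it.

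**The data.** At the randomisation visit (Study Procedures, item 3): "Blood (10mls) will be drawn to check for HIV viral load and CD4 count". The CD4 Report form has a box for the "Randomization/LEEP Visit". The Randomization form records current ART use and the original start date. At the 6, 12, 18 and 24 month visits (item 5), "Blood (5 mls) will be drawn to check for CD4 count", and the Follow-up Form records ART started or changed since the previous visit.

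**The concern.** A chi-square on percentages cannot control for anything, so the primary analysis and the promise do not fit together. Nor does the promise belong only to the shedding ANCOVA, because its own paragraph discusses the effect of ART on recurrence.

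The time point is open as well. An analyst looking for the CD4 covariate finds only the follow-up draws mentioned in the analysis text, and an undated reference to clinic files for ART. Either could lead to a randomised comparison being conditioned on values that arose after allocation, which no longer estimates a clean effect of assignment.

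Two things are at stake. First, an open choice of model in a trial whose investigators and staff are not blinded leaves room for that choice to follow the results. Interim Efficacy Analyses applies O'Brien-Fleming boundaries to the primary outcome without naming the test statistic, so the same gap reaches the monitoring. Second, the plan collects candidate prognostic data at baseline and gives them no role in the primary comparison.

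**Working it through.** **1. The plan's own figure.** Inputs from Statistical Methods: 4% versus 14%, 80% power, 0.05 significance (two-sided assumed), 20% loss, 400 women.

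- Per arm: [1.960 × √(2 × 0.09 × 0.91) + 0.842 × √(0.04 × 0.96 + 0.14 × 0.86)]² / 0.10² = 127.4, so 128.
- After loss: 128 / 0.8 = 160 per arm, 320 in total.
- With continuity correction: 147, then 184 per arm, 368 in total.

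The stated 400 exceeds both. The difference is on the conservative side and has no bearing on this point. With 200 randomised and 20% lost, 160 per arm are evaluable, and the formula gives 88.2% power for the unadjusted test.

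**2. Information available for adjustment.** Expected events are 160 × 0.04 + 160 × 0.14 = 6.4 + 22.4 = 28.8.

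- Arm, CD4, ART presence and ART duration: 28.8 / 4 = 7.2 events per parameter.
- With contraceptive history as one further term: 28.8 / 5 = 5.8.

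**3. What baseline adjustment would gain.** The documents give no covariate effects, so they are assumed: the same odds ratio for CD4 (per SD) and for ART, set at 1, 1.5, 2 or 3. ART prevalence is 75%, as the plan expects. ART duration is fitted but given no effect. The comparison is the chi-square against a likelihood-ratio test from a logistic model with baseline CD4, ART and ART duration, at 160 per arm, with 4,000 simulated trials per scenario.

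| Odds ratio | Power, chi-square | Power, adjusted | Gain (points) | Type I, chi-square | Type I, adjusted |
|---|---|---|---|---|---|
| 1 | 89.88% | 90.28% | 0.40 | 5.15% | 5.35% |
| 1.5 | 90.40% | 91.45% | 1.05 | 5.15% | 5.33% |
| 2 | 89.50% | 90.90% | 1.40 | 4.53% | 5.48% |
| 3 | 90.35% | 93.73% | 3.38 | 4.98% | 5.75% |

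Power is at 4% versus 14%; type I error is at 9% in both arms. The simulation standard error is about √(0.9 × 0.1 / 4000) = 0.5 points for power and √(0.05 × 0.95 / 4000) = 0.3 points for type I error. At an odds ratio of 1 the covariates carry no information, so the 0.40 there cannot be a precision gain. Part of the other gains may likewise reflect the adjusted test's slightly higher error rate.

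**4. Chance imbalance in ART.** No stratification by ART or CD4 is stated. With 75% on ART and 200 per arm, the SD of the between-arm difference is √(2 × 0.75 × 0.25 / 200) = 4.3 points, and 1.96 × 4.3 = 8.5 points is exceeded in about 5% of randomisations. Assuming 9% recurrence overall and an ART odds ratio of 1.5 to 3, recurrence on and off ART differs by about 3.6 to 10.6 points. A gap of 8.5 points then shifts the arm difference by 0.085 × 3.6 = 0.3 to 0.085 × 10.6 = 0.9 points, against a design difference of 10.

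**The case against.** The strongest reply is that an unadjusted test is legitimate in a randomised trial and keeps its error rate (4.5 to 5.2% above). Chance imbalance is already allowed for in that rate, and the plan itself thinks ART may have little effect on recurrence. All of that stands. A reader might infer that the primary test is biased, or that adjustment is the only protection against imbalance; neither follows.

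A reader might also infer that the plan will adjust for follow-up CD4. The documents do not say so. The follow-up sentence describes data collection, comes after the promise, and does not exclude the randomisation draw. What stands is that it is the only CD4 source named in the analysis text, so the covariate is not fixed.

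It is tempting to add that a follow-up CD4 covariate would cost up to the planned 20%, or 80 of 400 women. That does not hold. CD4 and the Pap smear are taken at the same visits, so a woman lost before a visit lacks the outcome there too. The extra loss would be draws missed at attended visits, for which the documents give no figure.

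Finally, moving to an adjusted ratio measure would leave the risk-difference scale on which the trial was sized, and a Cox model is not needed to remove the conflict. Both points stand and shape the fix. The reply does not reconcile the promise with the test.

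**Conclusion.** The point holds as a specification defect that should be corrected. The promised control for CD4 and ART cannot be delivered by the stated primary analysis, no alternative model for recurrence is defined, and the timing of the covariates is open. The chi-square itself remains valid.

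The benefit of using the baseline values is modest, at about 0.4 to 3.4 points of power. That range rests on 160 evaluable women per arm, the design rates of 4% and 14%, and assumed odds ratios of 1 to 3. Up to an odds ratio of 2 it is no more than 1.4 points. A claim of a large precision gain would need a covariate effect that the documents do not supply. The main reason to act is that one adjusted analysis, fixed in advance, removes a contradiction and a post hoc choice using data already scheduled for collection.

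**What to change.** In Statistical Methods:

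- Pre-specify one baseline-adjusted comparison of recurrence by arm, for example logistic or discrete-time, reported as a standardised risk difference so that the 4% versus 14% scale is kept.
- Fix a short covariate set: CD4 at randomisation, in a stated form, and ART at randomisation. Code ART duration in categories that include not on ART, since duration is undefined for the roughly 25% expected to be off treatment. Three ART categories plus CD4 and arm make four parameters, or 7.2 events each.
- State the ART data source with the randomisation date as cut-off, and a rule for unknown start dates. The Randomization form allows that answer, while the analysis text relies on clinic files.
- State that follow-up CD4 and later ART changes do not enter the treatment-effect model.
- Say which analysis contraceptive history belongs to; in this one it would reduce the ratio to 5.8 events per parameter.
- Report the unadjusted chi-square alongside, and name which of the two is primary and is the statistic used under Interim Efficacy Analyses. Keeping the chi-square primary with the adjusted model as supportive also resolves the conflict.

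The cost is plan wording, a little extra analysis and agreement with the DSMB on the monitored statistic. No new data collection is needed.
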